#### **4.5 Specimen collection procedures**

##### *4.5.1 Timing and volume of blood draw*

All participants will have a blood samples collected at four time-points and urine samples at two time-points (if not already available as part of routine clinical care). Blood will be obtained by venipuncture, or from an existing venous or arterial catheter. Urine will be collected via clean catch urine or via catheter.

##### Specimen Collection Time Points

1. T1=0 hrs (just before study drug administration)
2. T2=24 hrs (+/- 2 hrs)
3. T3=72 hrs (+/- 2 hrs)
4. T4=120hrs (+/- 12hrs)

##### *4.5.2 Specimen samples*

At the T1, T2, T3, and T4 time points, blood will be sent for complete blood count (including hemoglobin, white blood cell count, platelet count), a serum chemistry (including sodium, potassium, chloride, bicarbonate, blood urea nitrogen, creatinine, glucose, aspartate transaminase, alanine transaminase, and total bilirubin), and a venous blood gas to measure lactate. These tests will be performed by the clinical laboratory at each site. As many of these laboratory tests are commonly obtained for clinical purposes, these tests do not need to be repeated if a result is available from the clinical care of the participant within 2 hours of the time point (or within 12 hours of the T4 time-point).

In addition to traditional clinical markers, blood will be obtained for future biomarker analysis (including inflammatory biomarkers, markers of endothelial function, and markers of mitochondrial function), and measurement of vitamin C, vitamin B1, and cortisol levels. The total volume of blood that may be drawn for a participant at each time point will not exceed 60mls. Levels of vitamin C, vitamin B1, and cortisol will be measured at time T1 and time T3 only. 20ml of urine will be collected for future biomarker analysis at T1, T2, and T3.

[figure not shown]
If performed as part of standard-of-care, results of urinalysis and urine sediment testing will be collected prior to enrollment.

#### 4.5.3 Biomarker tube initial processing and shipping

Please see accompanying blood collection standard operating procedure for full details. In brief, 15ml of blood will be drawn into EDTA tubes and 10ml of blood will be drawn into a corvac tube. From one of the EDTA tubes, 3ml of whole blood will be initially drawn and separated into 3x 1ml aliquots. Plasma will then be isolated from the EDTA tube(s) and aliquoted into cryovials as follows: 4x 0.5ml aliquots and the remainder in 1ml aliquots. Serum will then be isolated from the corvac tube, and separated into 1ml aliquots. Cryovials will be protected from light and frozen at -80°C until processing. An additional 20ml of urine will also be collected, centrifuged, and separated into 1ml aliquots then frozen at -80°C until processing.

Sites will be expected to ship frozen samples to the coordinating center after every 5 enrollments. The coordinating center will assist with all shipping procedures.

#### 4.6 Study flow diagram

#### 4.7 General Sepsis Management

Investigators should follow local sepsis management guidelines. No specific sepsis bundle is required by this study, however the early administration of antibiotics, maintenance of a mean arterial pressure  $\geq 65$ mmHg with a combination of volume resuscitation and vasopressors, and early source control are recommended—as detailed in the Surviving Sepsis Guidelines. Elements of sepsis care should be reported on the online case report form (CRF).

#### 4.8 Glucometer use during the study period

High dose vitamin C has been shown to falsely elevate glucose level readings when measured with certain point-of-care glucometers employing glucosedehydrogenase-pyrroloquinoline quinone amperometric methods. Some commonly used glucometer brands using this approach include Accu-Chek (Roche Diagnostic) and Optium (Abbott Diabetes Care) (but not StatStrip; Nova Biomedical). While the effects of high-dose vitamin C on glucometer readings have been seen primarily at higher doses of vitamin C than are intended for use in this trial, we recommend that sites explore what glucometers are in use in local ICUs. If locally used glucometers may be impacted by high serum concentrations of vitamin C (as determined by the manufacturer), we recommend that clinical teams caring for enrolled participants be alerted to the possibility of falsely elevated blood-glucose levels when measured by glucometer. If there is a clinical concern about a glucose reading obtained via glucometer, a serum glucose should be obtained which will not be impacted by vitamin C. In the event of an emergency related to suspected hypoglycemia, glucose should be immediately given while a serum glucose level is pending.

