### 5.4.2 Specific adverse event data collection

To assess specific and potentially serious adverse events that may be related to the combination of the study medications, we will collect data on the following:

Serious Adverse Event	Definition
Hyperglycemia	Serum glucose >300mg/dl in the first 120-hours after enrollment
Hypernatremia	Serum sodium (> 150 mmol/L) occurring in the first 120-hours after enrollment
New Infection	As determined by the site principal investigator at each site. Should be a new organism or site of infection and believed to be unrelated to the initial presenting infectious source. Many will have the initiation of new antibiotics or a change in antibiotics.
Catheter-site	
Lung	
Gastrointestinal	
Urinary tract	
Other	
Serious allergic reaction	Anaphylaxis or other allergic reaction requiring systemic corticosteroids. Allergic reaction should be related (or suspected to be related) to the study medication
Renal calculus	Development of a renal calculus between enrollment and 30-day follow-up (based on question asked during follow-up phone call).

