### 5.4.3 Adverse Event Reporting

All unexpected serious adverse events thought to be related to the study drug, and any unexpected fatal or life-threatening adverse events thought to be related to the study drug will be recorded in the online CRF, reported directly to the coordinating center, and reported to the appropriate IRB shortly following the event per local protocol. In addition, unexpected serious adverse events related to the study drug will be undergo expedited reporting to the DSMB within 7 days of the coordinating center becoming aware of the event. The DSMB will additionally review all adverse events in aggregate after every 50 patients are enrolled.

Adverse events will additionally be reported to the FDA as outlined in 21CFR312.32 and summarized below:

- a. All unexpected fatal or life-threatening adverse events thought to be related to the study drug will be reported to the FDA within 7 calendar-days of when the ACTS team is made aware of the event.
- b. All unexpected serious adverse events thought to be related to the study drug will be reported to the FDA within 15 calendar-days of when the ACTS team is made aware.
- c. All serious unexpected adverse events, and any unexpected fatal or life-threatening events thought to be related to the study drug, will be reported back to all site investigators within 15 calendar-days of the event.
- d. The ACTS team will periodically review all published information relating to the safety of each element of the drug combination. Any concerning safety information obtained from this review, or otherwise obtained (e.g. from unpublished scientific papers), will be reported to the FDA within 15 calendar-days.

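### Section 4.8 anticipates falsely high glucometer readings and suspected hypoglycemia, but the safety table in 5.4.2 defines a glucose event only in the high direction, so low glucose has no planned between-arm comparison

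*Protocol*

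**What the plan says.** **Protocol 4.8.** The section opens with the measurement problem: "High dose vitamin C has been shown to falsely elevate glucose level readings when measured with certain point-of-care glucometers". It then limits it. The effect has been seen "primarily at higher doses of vitamin C than are intended for use in this trial", and it concerns particular devices, some of which the section describes as in common use. Sites are advised to find out which meters their ICUs use. If those may be affected, the authors "recommend that clinical teams caring for enrolled participants be alerted to the possibility of falsely elevated blood-glucose levels when measured by glucometer". When a bedside value is in clinical doubt, the section calls for a serum measurement, which it says vitamin C does not affect. The section closes: "In the event of an emergency related to suspected hypoglycemia, glucose should be immediately given while a serum glucose level is pending".

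**Protocol 5.4.2.** This table collects specific, potentially serious events that the study medications may cause. Its rows are hyperglycemia, hypernatremia, new infection, serious allergic reaction and renal calculus. The hyperglycemia row reads "Serum glucose >300mg/dl in the first 120-hours after enrollment". There is no row for low glucose and no low cut-off.

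**Protocol 5.4.3 and 6.2.3.** Individual reporting covers "All unexpected serious adverse events thought to be related to the study drug" and fatal or life-threatening events of the same kind. The DSMB also looks at adverse events in aggregate after every 50 enrolments. Section 6.2.3 has adverse events analysed like renal failure, that is, by Fisher's exact test.

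Sections 4.8 and 5.4.2 of the SAP match the protocol on all of this.

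**The concern.** Only the active arm receives study vitamin C (2.3.1, 2.3.2), so any distortion of bedside readings by study drug would fall on one side of the randomized comparison. The protocol took this seriously enough to give it a section, and that section ends by contemplating suspected hypoglycemia. The table meant to hold possible drug-related harms looks only the other way.

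The high-glucose row is well founded, since 8.1.2 names hyperglycemia as a risk of hydrocortisone. It also rests on serum glucose, which 4.8 says vitamin C does not affect. The gap is the missing counterpart. If low glucose occurred more often in the active arm, the plan as written has no defined event to count, to put before the DSMB by group, or to test at the end. The final report could describe glucose safety without addressing the direction that prompted 4.8.

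**Working it through.** The plan states no figure on this point, so there is none to reproduce. The check sets the sections side by side and then sizes the partial substitutes and the proposed item.

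**1. What would bring a low glucose into a comparison?**

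- *Specific-event table (5.4.2):* serum glucose above 300 mg/dL only. A low value cannot meet it.
- *Individual reporting (5.4.3):* the event must be serious, unexpected and thought to be drug-related. Clinical staff and investigators are blinded (2.4), so the relatedness judgement is made without knowing the arm.
- *Aggregate DSMB review (5.4.3, 9.2):* covers adverse events that are recorded. Neither section defines low glucose as one.
- *Final analysis (6.2.3):* Fisher's exact test on adverse events, which needs a defined binary event.
- *Scheduled serum chemistry (4.5.2):* includes glucose at T1 to T4, measured by the clinical laboratory. No by-arm analysis of it is described.

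**2. How much does scheduled serum glucose cover?**

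Inputs: 100 per arm (6.1); dosing for 4 days = 96 h (2.3.1); T2 = 24 h ± 2, T3 = 72 h ± 2, T4 = 120 h ± 12 (4.5.1).

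- Post-baseline values, both arms: 3 x 200 = 600.
- T4 falls at 108 to 132 h, which is 12 to 36 h after a full 96 h course. Only T2 and T3 are on treatment.
- On-treatment values, both arms: 2 x 200 = 400.
- On-treatment values, active arm: 2 x 100 = **200 at most**. There will be fewer in practice, because study drug stops at death or on leaving the ICU (4.4).

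This is two values per active participant, 48 h apart. A brief low between draws would usually be missed.

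**3. What could a defined event show?**

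Fisher's exact test, two-sided 0.05, 100 per arm. As a check on the method, exact enumeration at the plan's own renal failure rates (30% vs 55%) gives 93.9% power, against the stated 94%.

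Smallest significant split against zero events, with p = 2 x C(100,k) / C(200,k):

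- k = 5: p ≈ 0.059, not significant.
- k = 6: p = 2 x (100·99·98·97·96·95) / (200·199·198·197·196·195) ≈ 0.029, significant.

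The documents give no low-glucose rates. Under assumed rates:

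| Placebo | Active | Power |
|---|---|---|
| 2% | 5% | 10% |
| 2% | 10% | 59% |
| 5% | 10% | 19% |
| 5% | 15% | 59% |
| 5% | 20% | 88% |
| 10% | 20% | 44% |
| 10% | 25% | 76% |

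Only a large difference would be detected reliably. The main yield is a count by arm.

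**The case against.** The strongest reply is that this is an optional addition to a list the sponsor was free to choose, for a risk the protocol itself marks down. Section 4.8 confines the effect to certain meters and says it was seen mainly at higher doses. The direction that is tracked is the documented effect of hydrocortisone. Serum glucose is already drawn and could be tabulated by arm. The adverse event definition in 5.4.1 is broad, 6.2.3 is not limited to the 5.4.2 list, and a severe hypoglycemic event could be reported under 5.4.3. The CRF and the DSMB charter are not in the documents, so low glucose may be collected there. With low power, a new row would be descriptive.

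Much of this stands, and it rules out stronger readings that a reader might be tempted to make:

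- *That the trial's own dose is said to distort bedside glucose.* The dose and device qualifiers do not support that, although a statement about where the effect was mainly seen does not exclude the trial dose.
- *That low glucose cannot surface in any comparison.* The scheduled values and the aggregate review are routes by which it could.
- *That the plan forecasts overtreatment and unrecognised hypoglycemia.* Section 4.8 gives a contingency instruction. The causal chain is an inference from it.
- *That all 600 post-baseline values bear on the exposure.* At most 200 do.

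The reply does not supply a planned comparison. Data that could be compared are not a pre-specified event, aggregate review sees only what is recorded, and the 5.4.3 route turns on blinded attribution. Low power does not count heavily against a safety row, because 5.4.2 already lists a serious allergic reaction, an event that is likely to be rare.

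**Conclusion.** The point holds in a limited form. The protocol and SAP anticipate falsely high glucometer readings and suspected hypoglycemia, yet they define a glucose event only above 300 mg/dL. Low glucose has no pre-specified event and no planned between-arm comparison. Scheduled serum glucose (at most 200 on-treatment active-arm values) and individual reporting of unexpected related events substitute only in part.

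This is a gap in safety capture that should be closed because closing it is cheap. It does not touch the primary or key secondary analyses, and nothing in the documents contradicts itself here. The size of the underlying risk cannot be estimated: the documents give neither low-glucose rates nor the share of participants at sites with affected meters, which could be anywhere from 0 to 100%. The conclusion concerns the protocol and SAP text alone and assumes nothing about the contents of the CRF or the DSMB charter.

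**What to change.** Add a low serum glucose row to 5.4.2 in the protocol and SAP:

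- cut-off set by the sponsor;
- laboratory-measured serum values only, so that the item is free of the meter effect;
- the same 120-hour window and record source as the hyperglycemia row.

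Report it by group (masked, as 9.2 provides) in each 50-patient DSMB report, and by arm in the final adverse event table with the Fisher comparison of 6.2.3. Tabulating the scheduled serum glucose by arm and recording the glucometer type would help interpretation.

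The burden is small. The hyperglycemia row already requires sites to look at serum glucose over the first 120 hours, and 7.1 takes laboratory results from the medical record. That holds if the row is read as covering any serum value in the window. If it covers scheduled draws only, the new row inherits the sparse coverage shown above, so the table should say which is meant.

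The downside is one more safety comparison with few expected events and low power, to be read mainly as a count. The change affects what is recorded and reported; glucose management stays as it is.

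### Meter-prompted serum glucose tests may make detection of the hyperglycemia event differ by arm; size and direction are unknown, and a comparison at T2 and T3 is a cheap check

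*Protocol*

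**What the plan says.** Protocol section 4.8 warns: "High dose vitamin C has been shown to falsely elevate glucose level readings when measured with certain point-of-care glucometers". It qualifies this by saying the effect was "seen primarily at higher doses of vitamin C than are intended for use in this trial", and it names one meter brand that is not affected. Where local meters may be affected, it recommends that "clinical teams caring for enrolled participants be alerted to the possibility of falsely elevated blood-glucose levels when measured by glucometer". Doubt about a meter reading is to be settled by the laboratory: "If there is a clinical concern about a glucose reading obtained via glucometer, a serum glucose should be obtained". The section adds that vitamin C does not affect the serum value. No numeric reading is given at which this should happen.

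Protocol section 5.4.2 defines hyperglycemia as "Serum glucose >300mg/dl in the first 120-hours after enrollment". The definition is not limited to scheduled samples. Section 4.5.2 schedules a serum chemistry, including glucose, at T1 to T4 (0, 24, 72 and 120 hours). It lets a clinical-care result within 2 hours of a time point (12 hours for T4) stand in for the scheduled draw. Section 7.1 takes laboratory results from the medical record.

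Sections 6.2.2 and 6.2.3 compare adverse events by arm as renal failure is compared, with Fisher's exact test. Nothing accounts for how often serum glucose was measured. The SAP repeats these rules under the same section numbers.

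**The concern.** The event can be recorded only when a serum glucose is sent. Between scheduled draws, one thing that can prompt a serum test is the bedside meter, and on some meters the reading may depend on vitamin C, which as study drug only the active arm receives. A true episode above 300 could then be confirmed in one arm and treated without confirmation in the other. Blinding does not prevent this, because the reading that raises the question may itself depend on the arm.

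Protocol section 8.1.2 names hyperglycemia as a possible effect of hydrocortisone, and the DSMB reviews aggregate adverse events after every 50 participants (section 5.4.3). The planned crude comparison could not separate a steroid effect from a difference in testing.

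**Working it through.** The documents give no hyperglycemia rate, no meter bias at the trial dose, no share of sites with affected meters and no testing frequency. There is thus no stated figure to reproduce, and every glucose input below is an assumption. From the documents come only 100 participants per arm, the two-sided 0.05 level, Fisher's exact test, the 300 mg/dL cut-off and the sampling times.

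**Detection model, with no true difference between arms.** Let b be the share positive on scheduled draws, e the share with another episode above 300 between draws, and c the chance that such an episode gets a serum test.

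- Recorded event rate = 1 - (1 - b)(1 - e·c)
- Spurious difference, active minus placebo = (1 - b) · e · (c_active - c_placebo)

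Take b = 0.10 and c_placebo = 0.40. With e = 0.25 the placebo rate is 1 - 0.90 × (1 - 0.10) = 19.0%. If c_active = 0.60, the active rate is 1 - 0.90 × (1 - 0.15) = 23.5%. The rejection probability is an exact enumeration of Fisher's test at 100 per arm.

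| e | c_active | Placebo rate | Active rate | Difference (points) | Fisher rejects |
|---|---|---|---|---|---|
| 0.25 | 0.40 | 19.0% | 19.0% | 0 | 3.3% |
| 0.25 | 0.30 | 19.0% | 16.75% | -2.25 | 4.8% |
| 0.25 | 0.50 | 19.0% | 21.25% | +2.25 | 4.7% |
| 0.25 | 0.60 | 19.0% | 23.5% | +4.5 | 8.9% |
| 0.15 | 0.50 | 15.4% | 16.75% | +1.35 | 3.9% |
| 0.35 | 0.30 | 22.6% | 19.45% | -3.15 | 6.0% |
| 0.35 | 0.70 | 22.6% | 32.05% | +9.45 | 26.9% |

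The 30% rows stand for alerted teams who discount high readings. The 50% row at e = 0.25 also describes a 40% v 60% gap when half the participants are at sites with affected meters, since 0.5 × 4.5 = 2.25.

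**Dependence on the reading that prompts a test.** A simulation gave both arms the same true glucose: person means 175 mg/dL (SD 45), within-person SD 45 with correlation 0.5 between 6-hourly values, and meter noise SD 15. Serum was drawn at 24, 72 and 120 hours and whenever the meter passed a trigger. The true share ever above 300 was 18.4% in both arms. The recorded share, by meter bias in mg/dL, was:

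| Trigger reading | Bias 0 | +25 | +50 | +100 |
|---|---|---|---|---|
| 250 | 18.4% | 18.4% | 18.4% | 18.4% |
| 300 | 16.7% | 18.3% | 18.4% | 18.4% |
| 350 | 8.0% | 11.7% | 16.6% | 18.4% |
| 400 | 6.3% | 6.6% | 8.0% | 16.6% |

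Placebo is the zero-bias column. With a trigger of 250 there is no difference at any bias. At 300 the largest gap is 18.4 - 16.7 = 1.7 points. Large gaps need teams to leave readings above 300 unconfirmed. Counting scheduled draws alone gives 6.2% in both arms at any bias. The simulation does not model treatment given in response to a false reading.

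**The case against.** A reader might infer that the plan will inflate hyperglycemia in the active arm, or that the comparison cannot be interpreted at all. The documents support neither reading.

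- Section 4.8 places the interference mainly above the trial dose and on certain meters only.
- The prompt is a discretionary clinical concern about a reading. In context it may be chiefly a check on meter accuracy. A test sent because a low glucose might be masked will not return a value above 300.
- Serum glucose is stated to be unaffected by vitamin C, so no false event is created. Only the detection of true events is in question.
- A true value above 300 already reads high on an unaffected meter, so it may well be confirmed on placebo too.
- Alerted teams may discount high readings, and treatment of a falsely high reading could lower true glucose. Either would push the difference the other way.
- This is one listed safety event, and no power claim rests on it.

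All of this stands, and it limits the point to a possibility of unknown size and sign. It does not close the gap. The event definition is still open to unscheduled tests, some of those tests may be prompted by an arm-dependent reading, and the analysis does not allow for it.

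**Conclusion.** The point holds in a limited form. At sites with affected meters, detection of true between-draw episodes may differ by arm. Under the assumed inputs the spurious difference runs from -3.15 points (-2.25 in the central reverse case) through zero to +9.45. Fisher's test exceeds its nominal 5% only in the more extreme part of that range. The difference vanishes if serum tests are sent at readings well below 300. None of these figures is an estimate for this trial, because the documents supply none of the glucose inputs. The primary and key secondary comparisons do not use this event. The added analysis is a cheap improvement to how one safety comparison can be read.

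**What to change.** In sections 5.4.2 and 6.2.3, and the matching SAP text, keep the any-value count and add a supplementary by-arm comparison of serum glucose above 300 mg/dL. It should use only the protocol-timed T2 and T3 values, among participants with the sample.

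- State how deaths before 24 or 72 hours and missing draws are handled.
- Flag any clinical-care result used in place of a scheduled draw, since such a test could itself have been meter-prompted.
- Report the number of serum glucose tests by arm if unscheduled tests are captured in the database. The case report form is not shown, so this part may need extra data collection.

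T2 and T3 fall inside the planned 4-day dosing period, although study drug stops earlier if the participant leaves the ICU. T4 is left out because "T4=120hrs (+/- 12hrs" runs from 108 to 132 hours: it comes after planned dosing and can fall beyond the 120-hour event window.

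The T2 and T3 values are already due to be collected, so the main cost is analysis wording and the flag. There are two downsides. Two fixed times miss peaks between draws, which is why the any-value count stays. The comparison also does not remove any effect of treatment given for falsely high readings. No clinical rule in section 4.8 needs to change.
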